4 STUDY SUBJECTS

4.1 Analysis sets

The list of subjects to be included in each of the analysis set is to be agreed between the Syne qua non statistician and Blue Earth Diagnostics once all study data are available and prior to database lock.

Enrolled Set: All subjects who entered screening.

Safety Analysis Set (SAF): All subjects who have been included in the database and have been administered fluciclovine (¹⁸F) will be included in the Safety Analysis Set (SAF).

Full Analysis Set (FAS): All subjects enrolled who have had a fluciclovine (¹⁸F) PET/CT scan will be included in the Full Analysis Set (FAS).

Evaluable Analysis Set (EAS): All subjects from the FAS who have an intended treatment management plan completed and a revised management plan page completed will be included in the Evaluable Analysis Set (EAS).

Per Protocol Set (PPS): All subjects in the EAS without major significant deviation following review of the protocol deviation list.

4.2 Disposition of Subjects

The number and percentage of all subjects enrolled, included in each analysis set, who completed the study and who prematurely withdrew, including a breakdown of the primary reasons for withdrawal, will be presented.

All enrolled subjects will be listed indicating their membership to the evaluable analysis set along with the reason for exclusion.

Completion and withdrawal information will be listed, including individual reasons for withdrawal.

Date: 10OCT2018 Version: Amendment 1 Final

4.3 Protocol Deviations

Failed inclusion criteria and failed exclusion criteria will be listed for screening failures.

The number and percentage of subjects within each deviation category will be presented by deviation type (Major Significant, Major or Minor) and by site and overall. The deviation category and type will be provided by Blue Earth Diagnostics. All protocol deviations will be listed.

4.4 Background and Demographic Characteristics

4.4.1 Demographic and Baseline Characteristics

Demographic characteristics (age, ethnic origin and race collected at Screening), body measurements (height, weight collected, and BMI derived at Visit 2) will be summarised for the enrolled set, FAS, EAS and PPS populations.

Body mass index (BMI) is calculated as (weight (kg)/height (m)²).

Individual demographic characteristics and body measurements data will be listed.

4.4.2 Medical History

Medical history events will be coded using the Medical Dictionary for Regulatory Activities (MedDRA) version 18.1.

The number and percentage of subjects from the FAS with previous medical history and current events will be tabulated by system organ class (SOC), preferred term (PT). SOCs will be ordered in decreasing frequency of the total number of subjects with medical history events reported in each SOC and PTs will be ordered within a SOC in decreasing frequency of the total number of subjects with each medical history event. This table will be repeated for all events, regardless of whether previous or current events.

All medical history events will be listed.

4.4.3 Prostate Cancer History

Details of prostate cancer history will be summarised for subjects from the FAS, and will consist of:

- Time since initial diagnosis (months), calculated as [12*(date of informed consent date of initial prostate cancer diagnosis + 1)/365.25]
- TNM stage: Pathological TNM stage if available, otherwise Clinical TNM stage. A summary for T1 total, T2 total and T3 total will be provided as the sum of the number of subjects in each of the subgroups plus any subjects where only T1, T2 or T3 was recorded.
- Gleason total score: Gleason total score from surgery if available, otherwise Gleason total score from biopsy
- Time since adjuvant treatment (months), calculated as [12*(date of informed consent stop date of adjuvant treatment + 1)/365.25]
- Duration of adjuvant treatment (months), calculated as [12*(stop date of adjuvant treatment – start date of adjuvant treatment + 1)/365.25]

- Time since diagnosis of biochemical recurrence (days), calculated as (date of informed consent – date of diagnosis of biochemical recurrence + 1). Time since diagnosis of BCR may be derived in months if more appropriate.
- Baseline PSA value
- Baseline PSA category (0 0.2, >0.2 0.5, >0.5 1, >1 2, >2 5, >5 10 and >10)

In addition, summary table to summarise baseline Prostate Specific Antigen (PSA) by Prior Radical Prostatectomy status (Prior Radical Prostatectomy vs No Prior Radical Prostatectomy) using descriptive statistics (number of subjects (n), mean, standard deviation (SD), minimum, median, and maximum), will be produced.

Details of prostate cancer history will be listed.

Date imputation for incomplete dates:

- If day part missing, put 15th of the month
- If day and month parts missing, put 01 July

4.4.4 Cancer Therapies for Prostate Cancer

Cancer therapies for prostate cancer will be coded according to the World Health Organization Drug Dictionary Enhanced (WHO DDE) (Enhanced) version Sep 2015.

Cancer therapies will be categorised as follows:

Subjects with radical prostatectomy:

- Radiotherapy
- No radiotherapy

Subjects without radical prostatectomy:

- Radiotherapy only
 - o EBRT only
 - Brachytherapy only
 - EBRT and brachytherapy
- Radiotherapy and other therapies
 - EBRT and other therapies
 - Brachytherapy and other therapies
- Other therapies

Prior cancer therapies for prostate cancer are defined as those for which the end date is prior to the date of injection of fluciclovine (¹⁸F).

Concomitant/post-scan cancer therapies for prostate cancer are defined as those with a start date on or after the injection date of fluciclovine (¹⁸F), or those with a start date before the injection date of fluciclovine (¹⁸F) but which continued with a stop on or after the injection date of fluciclovine (¹⁸F). Summaries for subjects with prior and post-scan radical prostatectomy will be presented separately.

Date: 10OCT2018 Version: Amendment 1 Final

Summary table to summarise time from ¹⁸F-fluciclovine PET/CT to first post-¹⁸F-fluciclovine treatment in days using descriptive statistics (number of subjects (n), mean, SD, minimum, median, and maximum) will be provided.

If cancer therapy dates are incomplete and it is not clear whether the medication was concomitant, it will be assumed to be concomitant.

The number and percentage of subjects per category of prostate cancer therapy will be presented for all subjects from the SAF, separately for subjects with and without radical prostatectomy. This summary will be repeated for prior and concomitant cancer therapies.

All therapies for prostate cancer will be listed including type of therapy, reported therapy name, medication class, standardised medication name, dose, dose unit, route of administration, start date and end date or 'ongoing' flag, therapy comments.

4.4.5 Prior and Concomitant Medications

Prior and concomitant medications will be coded according to the World Health Organization Drug Dictionary Enhanced (WHO DDE) (Enhanced) version Sep 2015.

Prior medications are defined as those for which the end date is prior to the date of injection of fluciclovine (18F).

Concomitant medications are defined as those with a start date on or after the injection date of fluciclovine (¹⁸F), or those with a start date before the injection date of fluciclovine (¹⁸F) but which continued with a stop date on or after the injection date of fluciclovine (¹⁸F).

If medication dates are incomplete and it is not clear whether the medication was concomitant, it will be assumed to be concomitant.

The number and percentage of subjects who took any medications will be presented by centre and overall by medication class, standardised medication names sorted alphabetically for all subjects from the SAF, separately for prior medications and concomitant medications.

All prior and concomitant medications will be listed including reported name, medication class, standardised medication name, indication, dose, dose unit, frequency, route of administration, start date and end date or 'ongoing' flag.

4.5 Administration of Investigational Product

The volume of undiluted fluciclovine, activity of fluciclovine and injection site reaction during and following fluciclovine administration will be summarised for subjects in the SAF.

5 EFFICACY EVALUATION

All listings will be based on the FAS unless specified otherwise. The primary efficacy analysis will be based on the EAS and will be repeated on the PPS as a secondary analysis. The secondary efficacy analyses will be based on the FAS.

Date: 10OCT2018 Version: Amendment 1 Final

5.1 **Primary Efficacy Variable**

The primary efficacy variable is the record of the revised management plan post fluciclovine (¹⁸F) PET/CT scan in comparison to the pre-scan intended management plan.

5.2 **Secondary Efficacy Variables**

The secondary efficacy variables are:

- The proportion of subjects who have a sustained response to radical salvage therapy.
- PSA levels in relation to scan positivity will be analysed to determine the optimal PSA threshold for detecting recurrent PCa by fluciclovine (18F) PET/CT.

Definition of Region Levels

Two main regions will be analysed, the prostate and prostate bed and the extraprostatic region.

The prostate and prostate bed include the following lesion locations:

- Prostate bed left
- Prostate bed right
- Peripheral zone left
- Peripheral zone right
- Central gland left
- Central gland right
- Left seminal vesicle
- Right seminal vesicle

The extra-prostatic regions include the following lesion locations

- Lymph nodes
 - Pelvic lymph nodes
 - Common iliac left
 - Common iliac right
 - Internal iliac left
 - Internal iliac right
 - External iliac left
 - External iliac right
 - Obturator left
 - Obturator right
 - Pre-sacral left

- Pre-sacral right
- Peri-rectal anterior
- Peri-rectal posterior
- Peri-rectal left
- Peri-rectal right
- Inguinal left
- Inguinal right

- Retroperitoneal lymph nodes
 - Para-aortic
 - Retro-aortic
 - Para-caval
 - Retro-caval
- Other lymph nodes
 - Intra-peritoneal
 - Mediastinal left
 - Mediastinal right
 - Axillary left
- Soft tissues/parenchyma
 - o Lung upper lobe left
 - Lung upper lobe right
 - Lung middle lobe right
 - Lung lower lobe left
 - o Lung lower lobe right
 - Brain left
 - o Brain right
 - Liver left
 - Liver right
 - Spleen
 - Subcutaneous/cutaneous
 - Muscle
 - Bowel
- Bones
 - o Skull
 - Skull base/maxilla left
 - Skull base/maxilla right
 - Mandible left
 - Mandible right
 - Vertebra
 - Vertebra C1
 - Vertebra C2
 - Vertebra C3
 - Vertebra C4

- Aorto-caval
- Retrocrural left
- Retrocrural right
- Axillary right
- Cervical left
- Cervical right

Vertebra C5

Vertebra C6

Vertebra C7

Vertebra T1

- Vertebra T2
- Vertebra T3
- Vertebra T4
- Vertebra T5
- Vertebra T6
- Vertebra T7
- Vertebra T8
- Vertebra T9
- Vertebra T10
- Vertebra T11

o Chest

- 1st rib left
- 1st rib right
- 2nd rib left
- 2nd rib right
- 3rd rib left
- 3rd rib right
- 4th rib left
- 4th rib right
- 5th rib left
- 5th rib right
- 6th rib left
- 6th rib right
- 7th rib left
- 7th rib right
- 8th rib left

Pelvis

- Ilium left
- Ilium right
- Superior pubic ramus left
- Superior pubic ramus right
- Inferior pubic ramus left

- Vertebra T12
- Vertebra L1
- Vertebra L2
- Vertebra L3
- Vertebra L4
- Vertebra L5
- Sacrum left
- Sacrum right
- Sacrum central
- 8th rib right
- 9th rib left
- 9th rib right
- 10th rib left
- 10th rib right
- 11th rib left
- 11th rib right
- 12th rib left
- 12th rib right
- Sternum
- Clavicle left
- Clavicle right
- Scapula left
- Scapula right
- Inferior pubic ramus right
- Pubic body left
- Pubic body right
- Ischium left
- Ischium right

Appendicular

- Proximal humerus left
- Proximal humerus right
- Proximal femur left
- Proximal femur right

5.4 Statistical Analysis

5.4.1 Primary Efficacy Analysis

The analysis of the primary outcome will be performed on the EAS as the primary analysis and will be repeated on the PPS as a secondary analysis. Comparisons between the original treatment plan and the revised treatment plan will be categorised as no change, major change or other change. The definitions of the change categories are listed below.

- No change: the original treatment plan is the same as the revised treatment plan
- Major change: the original treatment plan is not the same as the revised treatment plan and the grouping for the original treatment plan is not the same as the grouping for the revised treatment plan

These will be further split and presented according to the following categories:

- Salvage or Non-curative systemic therapy to Watchful waiting
- Salvage therapy to Non-curative systemic therapy
- Non-curative systemic therapy to Salvage therapy
- Alternative Major change
- Other change: the original treatment plan is not the same as the revised treatment plan but the grouping for the original treatment plan is the same as the grouping for the revised treatment plan

These will be further split and presented according to the following categories:

- Modified RT field plan
- Modified androgen-deprivation regimen
- Alternative Other change

Groupings of treatment plans are detailed in the following table:

Date: 10OCT2018 Version: Amendment 1 Final

Version: Amendment 1 Fina ST/form/010/6

Original Treatment Plan	Grouping for Original Tx Plan	Revised Treatment	Grouping for Revised Tx Plan
Was androgen deprivation therapy planned	Androgen Deprivation Therapy	Androgen deprivation therapy	Androgen deprivation therapy
		Watch and wait	Watch and wait
		Chemotherapy	Chemotherapy
Salvage radiotherapy to the prostate bed		Salvage radiotherapy to the prostate bed	
Salvage radiotherapy to the prostate bed, with boost to areas guided by conventional imaging	Salvage Radiotherapy	Salvage radiotherapy to the prostate bed, with boost to areas guided by conventional imaging	Salvage Radiotherapy
		Salvage radiotherapy to the prostate bed with boost to areas guided by fluciclovine (18F) PET/CT	
Salvage radiotherapy to the prostate bed and whole pelvis		Salvage radiotherapy to the prostate bed and whole pelvis	
Salvage radiotherapy to the prostate bed and whole pelvis, with boost to areas guided by conventional imaging	Salvage Radiotherapy	Salvage radiotherapy to the prostate bed and whole pelvis, with boost to areas guided by conventional imaging	Salvage Radiotherapy
		Salvage radiotherapy to the prostate bed and whole pelvis with boost to areas guided by fluciclovine (18F) PET/CT	

Original Treatment Plan	Grouping for Original Tx Plan	Revised Treatment Plan	Grouping for Revised Tx Plan
Salvage cryotherapy		Salvage cryotherapy	
	Salvage Cryotherapy	Salvage cryotherapy with boost to areas guided by fluciclovine (18F) PET/CT	Salvage Cryotherapy
Salvage brachytherapy		Salvage brachytherapy	
	Salvage Brachytherapy	Salvage brachytherapy with boost to areas guided by fluciclovine (18F) PET/CT	Salvage Brachytherapy
		Salvage brachytherapy with treatment plan guided by fluciclovine (18F) PET/CT	
Salvage HIFU		Salvage HIFU	
	Salvage HIFU	Salvage HIFU with treatment plan guided by fluciclovine (18F) PET/CT	Salvage HIFU
Salvage prostatectomy		Salvage prostatectomy	
	Salvage Prostatectomy	Salvage prostatectomy with targeted resection / sampling of fluciclovine (18F) positive areas outside conventional surgical field	Salvage Prostatectomy
Salvage prostatectomy and limited lymph node dissection		Salvage prostatectomy and limited lymph node dissection	

Original Treatment Plan	Grouping for Original Tx Plan	Revised Treatment Plan	Grouping for Revised Tx Plan
		Salvage prostatectomy and limited lymph node dissection with targeted resection / sampling of fluciclovine (18F) positive areas outside surgical field	
Salvage prostatectomy and extended lymph node dissection (including internal and external iliac, and obturator nodes)		Salvage prostatectomy and extended lymph node dissection (including internal and external iliac, and obturator nodes)	
		Salvage prostatectomy and extended lymph node dissection (including internal and external iliac, and obturator nodes) with targeted resection / sampling of fluciclovine (18F) positive areas outside surgical field	
		Targeted salvage treatment of fluciclovine (18F) positive extra-pelvic / bony areas	Targeted salvage treatment
		Other	Other

The classification and sub-classification of change in treatment management plan will be agreed prior to data base lock.

The number, percentage and exact 95% CI of subjects with and without a change in management plan after the fluciclovine (18F) scan results become available will be presented. In addition, the number and percentage of subjects with changes categorised as major or other will be presented. These summaries will be repeated separately for subjects with a positive and a negative fluciclovine (18F) scan and for subjects without prostatectomy and with prostatectomy.

Date: 10OCT2018 Version: Amendment 1 Final Page 17 of 22

The number, percentage and 95% CI of subjects who agreed to the revised management plan after fluciclovine (¹⁸F) scan results become available will be presented.

Details of the intended management plan, revised management plan and agreed management plan will be listed.

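### A scan that only confirms the planned target can be counted as a management change, because fluciclovine-guided options exist only in the revised-plan list and no written rule covers a guidance-only switch

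*SAP*

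**What the plan says.** SAP 5.4.1 uses three categories. The first is "No change: the original treatment plan is the same as the revised treatment plan". *Major change* requires a different plan and a different grouping. The third begins "Other change: the original treatment plan is not the same as the revised treatment plan but the grouping for the original treatment plan is the"; it covers plans that differ within one grouping. Neither *No change* nor *Other change* mentions target, field or boost site.

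The grouping table in the same section lists options available before and after the scan. Some salvage options stand only in the revised column, for example "Salvage radiotherapy to the prostate bed with boost to areas guided by fluciclovine (18F) PET/CT", "Salvage HIFU with treatment plan guided by fluciclovine (18F) PET/CT" and "Salvage brachytherapy with treatment plan guided by fluciclovine (18F) PET/CT". Each shares the grouping of its unguided counterpart. The revised column also repeats every pre-scan salvage option, including "Salvage radiotherapy to the prostate bed, with boost to areas guided by conventional imaging".

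The headline output is "The number, percentage and exact 95% CI of subjects with and without a change in management plan". The major/other split is given as numbers and percentages, with no CI stated. On adjudication the SAP says only: "The classification and sub-classification of change in treatment management plan will be agreed prior to data base lock".

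Protocol 7.7 asks the clinical team to record after the scan whether the plan is unchanged or altered, and why. Its examples of change include altered treatment approaches and radiotherapy plans.

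**The concern.** The primary endpoint is meant to measure whether the scan affects management. Take a patient planned for a boost to a lesion seen on conventional imaging. The fluciclovine scan shows the same lesion, and the boost goes to the same place. If the team selects the fluciclovine-guided boost, because that scan is now the one in use, the two plan entries differ within one grouping and the SAP definition gives *Other change*. The treatment has not changed; only the image credited with guiding it has.

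The error runs one way. No pre-scan plan can carry the fluciclovine wording, so a guidance-only switch can add a change but never remove one. Neither document tells sites which option to choose when the scan merely confirms the target, so the classification depends on recording habit in an open-label study. The any-change proportion is the only change proportion with a stated CI, and the interim stopping rule is written on the number of treatment changes.

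**Working it through.** **1. Which switches are guidance-only.** Setting the two columns of the SAP 5.4.1 table side by side:

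| Pre-scan plan | Revised plan | Grouping | Guidance-only possible? |
|---|---|---|---|
| Prostate-bed RT, boost by conventional imaging | Prostate-bed RT, boost by fluciclovine | Same | Yes |
| Bed and whole-pelvis RT, boost by conventional imaging | Bed and whole-pelvis RT, boost by fluciclovine | Same | Yes |
| HIFU | HIFU, plan guided by fluciclovine | Same | Yes |
| Brachytherapy | Brachytherapy, plan guided by fluciclovine | Same | Yes |
| RT, cryotherapy or brachytherapy with no boost | Same modality plus fluciclovine boost | Same | No: a boost is added |
| Prostatectomy options | Same plus resection or sampling of positive areas outside the surgical field | Same | No: different area |
| Any salvage plan | Targeted treatment of extra-pelvic or bony areas | Different | No: different target |

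The first four rows are the affected set. All keep their grouping, so all fall into *Other change* and none can reach *Major change*. The planned sub-categories of *Other change* (modified RT field, modified androgen-deprivation regimen, alternative) do not isolate them.

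**2. The plan's own interim figure.** Inputs from SAP 5.4.4 and Protocol 11.3: n = 85, stop for effectiveness if more than 45 change, 97.5% two-sided CI, lower limit to exceed 40%. The exact limits are Beta(0.0125; x, n − x + 1) and Beta(0.9875; x + 1, n − x).

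- x = 45: 45/85 = 52.9%, exact limits 40.3% and 65.3%. The stated lower limit of 40.3% reproduces. The stated upper limit of 62.3% does not (exact 65.3%, Wilson 64.6%, Wald 65.1%), but the rule uses only the lower limit.

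**3. Sensitivity of that rule.** Assumption: k of the counted changes are guidance-only, starting from the smallest stopping count, 46. The documents give neither k nor the actual count.

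| k | Count | Proportion | Exact 97.5% lower limit | More than 45? |
|---|---|---|---|---|
| 0 | 46/85 | 54.1% | 41.5% | Yes |
| 1 | 45/85 | 52.9% | 40.3% | No |
| 2 | 44/85 | 51.8% | 39.2% | No |
| 5 | 41/85 | 48.2% | 35.8% | No |
| 10 | 36/85 | 42.4% | 30.3% | No |

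Each case moves the proportion by 1/85 = 1.2 percentage points. Five move it by 5/85 = 5.9 points, about the ±6 points of precision for which SAP 3.4 sized the trial.

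**4. Chance of crossing the boundary.** Assumption: true change rate q = 40%, and a share r of truly unchanged patients is recorded under a guided option. The observed rate is q + (1 − q)r. For r = 0, 10%, 20% and 30% this is 40%, 46%, 52% and 58%, and the binomial probability of more than 45 of 85 is 0.6%, 8%, 39% and 80%. The larger shares would need many patients to hold one of the four affected plans, which the documents do not show.

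**The case against.** The strongest reply is that the SAP does not force the miscount. Every pre-scan salvage option remains in the revised list, so a team whose scan confirms the target can record the same plan and the patient is *No change*. The definition speaks of the plan being the same, not the wording; where the SAP intends text matching it says so, as Addendum 2 does for agreed therapy. Protocol 7.7 provides a record of unchanged or altered with a reason, and the classification is to be agreed before database lock, so individual cases could be reassigned. This stands in part. It defeats the reading that a confirming scan is always counted as a change. It does not supply a rule: SAP 5.4.1 does not refer to the team's own record, and the agreement before lock has no stated criteria.

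The affected set is also narrow. Protocol 3.1 reports low yield for CT and bone scan in this setting, which suggests, indirectly, that conventional-imaging boosts may be uncommon. Protocol 7.7 counts changed approaches, so some HIFU or brachytherapy plans guided by fluciclovine may be genuine changes. Both points stand, and they argue for a sensitivity analysis over a new primary definition.

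Finally, the major/other split and the plan listings already limit the harm. They do, but they neither separate guidance-only cases nor give *Major change* an interval.

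**Conclusion.** The point holds in a limited form: a guidance-only switch can be counted as a management change, and no written rule prevents it. The effect is confined to *Other change*, can only raise the any-change proportion, and does not touch *Major change*. Its size is unknown, because the documents do not say how many patients moved between the affected options.

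A reader might infer that the early stop for effectiveness was wrong. The documents do not support that. Protocol 11.3 says only that the count exceeded 45, and nothing shows that the classification in this SAP version, dated October 2018, was the one used at the interim. The boundary figures show how sensitive the rule is at its edge, not what happened. A reader might also infer that every fluciclovine-specific option is a mere relabel. That is not so: resection outside the surgical field, targeted extra-pelvic or bony treatment, and a boost where none was planned are real changes.

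This is an inexpensive improvement that bounds a one-directional bias, not a defect that overturns the primary result.

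**What to change.** Keep the primary definition. Add to SAP 5.4.1 a sensitivity analysis along these lines:

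- A guidance-only switch is one in which modality and field are the same before and after the scan and the two plans differ only in the fluciclovine guidance wording.
- In the sensitivity analysis such a switch counts as *No change*, unless the clinical team's entry of altered or unchanged, with its reason, shows a different target.
- The any-change proportion is reported both ways, each with an exact 95% CI, together with the number of guidance-only switches.
- The major-change proportion also receives an exact 95% CI.

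The rule rests on the option wording and the recorded reason because the documents do not show that pre-scan target sites were captured; reclassifying the primary endpoint by target might not be feasible. Addendum 2 describes analyses added after database lock, so at this stage the addition would be a further addendum, labelled post hoc.

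The cost is a small review of records already collected, one extra row and one extra interval. The downside for the sponsor is a second figure beside the headline that can be lower but not higher.

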11.3. Interim Analysis

A single interim analysis of the primary endpoint was performed in the first 85 evaluable patients. The number of treatment changes was greater than 45 (52.9%, with a 97.5% two-sided C.I. of 40.3%-62.3%, so the lower limit is over 40%), the trial recruitment was terminated early due to overwhelming effectiveness. If the number of treatment changes would have been 8 or fewer (9.4%, with a 97.5% two-sided C.I. of 3.6%-18.9%, so the upper limit in this population would have been below the 20% of the null hypothesis), the trial would have been terminated early due to futility.

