5.4.2.2 PSA threshold

The detection rate (DR) will be calculated as number of positive fluciclovine (¹⁸F) scan results/total number of scans.

Date: 10OCT2018 Version: Amendment 1 Final

The point estimate (expressed in percentage) of the DR will be presented at the region level and at the subject level. These rates will be presented for all subjects from the FAS and PPS, overall and across a range of baseline PSA values:

- 0 0.2
- \bullet >0.2 0.5
- \bullet >0.5 1.0
- \bullet >1.0 2.0
- \bullet >2.0 5.0
- \bullet >5.0 10.0
- >10.0

to determine the optimum PSA threshold for lesion detection. See section 2 General Principles for baseline definition.

The detection rates will also be summarised across the following baseline Gleason score categories: <=6, 7, 8 and >=9.

All fluciclovine (18F) and other imaging results will be listed.

Handling of Dropouts or Missing Data 5.4.3

Subjects who withdrew from the study prior to completion will be summarised. Withdrawn subjects will not be directly replaced and no imputation of missing data will be conducted.

5.4.4 **Interim Analyses and Data Monitoring**

A single interim analysis of the primary endpoint will be performed in the first 85 evaluable subjects. If the number of treatment changes is greater than 45 (52.9%, with a 97.5% two-sided CI of 40.3%-62.3%, so the lower limit is over 40%), the trial will be terminated early due to overwhelming effectiveness. If the number of treatment changes is 8 or fewer (9.4%, with a 97.5% two-sided CI of 3.6%-18.9%, so the upper limit in this population is below the 20% of the null hypothesis), the trial will be terminated early due to futility.

Examination of Subgroups

No subgroup analyses will be conducted during the study.

Site Specific Sub-study 5.4.6

A site specific sub-study will be conducted in order to compare the ordered subset expectation maximisation (OSEM) standard of care method of reconstructing PET/CT images with that of the Bayesian penalised likelihood method of PET/CT image reconstruction. The analysis of the sub-study results is beyond the scope of this SAP.

SAFETY EVALUATION

All safety evaluations will be performed on the safety analysis set (SAF) unless specified otherwise.

Date: 10OCT2018 Version: Amendment 1 Final

All safety tables will be presented by centre and overall.

Subjects will be included and counted in summary tables only if they have available data.

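### After an efficacy stop triggered by the first 85 patients, the primary change rate is reported with no stop-adjusted estimate and no split of those 85 from later patients

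*SAP*

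**What the plan says.** - **Interim rule.** SAP 5.4.4: "A single interim analysis of the primary endpoint will be performed in the first 85 evaluable subjects". The efficacy boundary is "If the number of treatment changes is greater than 45 (52.9%, with a 97.5% two-sided CI of 40.3%-62.3%, so the lower limit is over 40" per cent. The futility boundary is "If the number of treatment changes is 8 or fewer (9.4%, with a 97.5% two-sided CI of 3.6%-18.9" per cent.
- **Outcome.** Protocol 11.3 reports in the past tense that the efficacy boundary was crossed and that "the trial recruitment was terminated early due to overwhelming effectiveness". It does not give the exact count.
- **Primary result.** SAP 5.4.1 presents "The number, percentage and exact 95% CI of subjects with and without a change in management plan".
- **Population.** SAP 5.4.1: "The analysis of the primary outcome will be performed on the EAS as the primary analysis". SAP 4.1 defines that set: "All subjects from the FAS who have an intended treatment management plan completed and a revised management plan page completed will be included". It therefore contains the patients whose count triggered the stop.
- **Allowance for the stop.** None appears in the SAP text supplied. SAP 3.5, on changes from the protocol's planned analysis, does not mention the stop, and neither does Addendum 2. The first addendum is not in the supplied text.

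**The concern.** Stopping when a count is high selects for a high count. Some of the 46 or more changes in the first 85 patients may be favourable chance variation. An ordinary proportion does not remove it, and nothing in the planned tables lets a reader see how large it is.

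The size of the rate is what this trial delivers. The 171 patients were chosen for the precision of an estimate (SAP 3.4), and the cited choline rates of 40% and 46.7% (Protocol 3.3) invite comparison. A shift of a few points would change how the result reads against those figures, although not whether it exceeds 20%.

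**Working it through.** **1. Plan's own figures.** Sample size: 1.96² × 0.20 × 0.80 / 0.06² = 170.7, so 171; 171 / 0.95 = 180. Both agree with SAP 3.4. Exact (Clopper-Pearson) 97.5% limits for 8/85 are 3.65% to 18.97%, which match the stated 3.6% to 18.9% if truncated. For 45/85 they are 40.3% to 65.3%. The stated lower limit agrees. The stated upper limit of 62.3% does not, and Wilson (64.6%) and Wald (65.1%) do not give it either. That figure should be checked, but nothing below depends on it.

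**2. Model.** Let p be the true change rate and X1 ~ Binomial(85, p) the interim count. The trial stops for efficacy if X1 ≥ 46 and for futility if X1 ≤ 8; otherwise it continues to 171. Let m be the number of evaluable patients beyond the first 85 when recruitment stopped. The documents give neither p nor m, so both are assumed over ranges: p from 46.7% to 65%, and m = 0, 15 or 30.

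**3. Mean reported rate given the efficacy stop:** (E[X1 | X1 ≥ 46] + m·p) / (85 + m).

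Example at p = 0.50, where E[X1 | X1 ≥ 46] = 48.29:
- m = 0: 48.29 / 85 = 56.8%
- m = 15: (48.29 + 7.5) / 100 = 55.8%
- m = 30: (48.29 + 15) / 115 = 55.0%

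| True rate | P(efficacy stop) | Mean reported rate given stop, m = 0 / 15 / 30 | Bias (points) | Coverage of exact 95% CI given stop |
|---|---|---|---|---|
| 46.7% | 10% | 56.1 / 54.7 / 53.7% | 9.4 / 8.0 / 7.0 | 84 / 77 / 81% |
| 50% | 26% | 56.8 / 55.8 / 55.0% | 6.8 / 5.8 / 5.0 | 94 / 93 / 92% |
| 55% | 61% | 58.4 / 57.9 / 57.5% | 3.4 / 2.9 / 2.5 | 97 / 97 / 97% |
| 60% | 89% | 61.2 / 61.0 / 60.9% | 1.2 / 1.0 / 0.9 | 98 / 97 / 97% |
| 65% | 99% | 65.2 / 65.2 / 65.2% | 0.2 / 0.2 / 0.2 | 97 / 97 / 97% |

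The bias falls along each row as m rises, because later patients dilute the selection.

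**4. Averaged over stopping and continuing** (85 if stopped, otherwise 171). The largest bias is 1.1 points, near p = 53.5%. The lowest coverage is 93.9%, near p = 43%, where the lower limit is too high 3.8% of the time against a nominal 2.5%.

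**5. Against 20%.** P(X1 ≥ 46 | p = 0.20) is about 4 × 10⁻¹².

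**6. What adjusted estimates would look like.** If the trial stopped at exactly 46/85 (54.1%), the estimate adjusted for average bias is 53.0%. The conditional maximum-likelihood estimate solves E[X1 | X1 ≥ 46] + m·p = total observed changes. With an assumed m = 20 (105 patients):
- 57/105 (54.3%) becomes 46.5%
- 61/105 (58.1%) becomes 55.6%
- 63/105 (60.0%) becomes 58.7%
- 68/105 (64.8%) becomes 64.6%

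At exactly 46/85 with no later patients this equation has no solution, because 46 is the lowest count that stops the trial.

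**The case against.** The strongest reply is that an estimator should be judged over the whole design. On that view the plan is nearly sound, with bias of at most about 1.1 points and coverage of at least about 94%. Whether to condition on the stop is a recognised choice, and an unadjusted primary estimate is not an error. The large conditional figures also sit at true rates where the stop is uncommon: 26% at a true 50% and 10% at 46.7%. Where the stop is likely, at 55% or more, conditional coverage is about 97%. For a stop at exactly 85, the stage-wise exact interval equals the ordinary one. All of this stands. It is why the unadjusted analysis can remain primary.

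It does not remove the point. The stop is a known fact, and without the interim count or final number a reader cannot tell whether the correction is nil or several points. A pre-specified rule makes the stop legitimate; it does not make the estimate unbiased given the stop.

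A reader might infer three stronger things that the documents do not support:
- **The claim of effectiveness is in doubt.** It is not: at the 20% null in SAP 5.4.4 the stop is practically impossible.
- **Pooling causes the bias.** It reduces it. The gap is only that the parts are not also shown separately.
- **The final interval should be at 97.5%, or the bias should be set against the planned half-width of 6 points.** Neither document sets 97.5% for the final interval, and a wider interval leaves the point estimate unchanged. The 6 points belong to 171 patients at a 20% rate. At 46/85 the exact 95% CI is 43.0% to 65.0%, about 11 points each way.

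**Conclusion.** The point holds as a cheap improvement to reporting, not as a flaw in the trial's conclusion. The primary rate is unadjusted after a data-driven stop. Its likely overstatement, given the stop, depends on a true rate that the documents do not fix: about 5 to 7 points at 50%, 2.5 to 3.4 at 55%, about 1 at 60%, and negligible from 65%. Conditional coverage falls clearly below 95% only below a true rate of about 50%. Over the whole design the bias is at most about 1.1 points.

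These sizes rest on independent patients with a common change rate and on the assumed 0 to 30 later patients. The documents do not support saying that the reported rate is in fact several points too high: if the interim count was well above 46, the correction is trivial.

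**What to change.** In SAP 5.4.1 and 5.4.4:

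1. Keep the pooled EAS rate with its exact 95% CI as the primary result.
2. Show the rate and exact 95% CI side by side for the first 85 evaluable patients, the later patients and the pooled EAS, and state the interim count. The later patients are the only group not selected by the stop.
3. Add one sensitivity estimate with its CI that allows for stopping when more than 45 of 85 change. Name the method before computing it, for example the mean-bias-adjusted or the conditional maximum-likelihood estimate. The two can differ by several points near the boundary, so the choice should not follow the result.
4. If this is added after database lock, label it post hoc. Addendum 2 already added tables at that stage, so the route exists.

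Cost: one extra table and a short addendum, with no new data. The sensitivity rate may be slightly lower than the headline, and the interval for the later patients will be wide if they are few.
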